#### 5.5 **30-day Safety Follow-up visit**

All patients will be followed for a minimum of 30 days after the last dose of derazantinib. During the 30-day safety follow-up period, AEs and changes in concomitant medication should be reported.

Patients with unresolved study drug-related AEs (occurred during the study treatment period or the 30-day safety follow-up period) will be followed until, in the opinion of the Investigator, study drug related toxicities have resolved to baseline, CTCAE Grade 1, stabilized, or are deemed to be irreversible. A study drug-related AE is defined as an AE that is definitely, probably, or possibly related to the treatment with derazantinib, or when the relationship is unknown. If a patient receives other anti-cancer therapy within the 30-day safety follow-up period, the follow-up for AEs will cease, beginning the first day of the new therapy.

\* Patients who develop ocular symptoms or changes in visual acuity while on the study should be referred to an ophthalmologist for a complete eye examination.

In addition, at the 30-day Safety Follow-up visit, the following assessments will be made:

- EORTC QLQ-C30 and QLQ-BIL21, and EQ-5D, questionnaires (should be completed by the patient prior to being evaluated by the physician) (see Section 6.10 and Appendix 7)
- Physical examination (see Section 6.2)
- Complete opthalmological examination (see Section 6.3)
- Vital signs (weight, temperature, blood pressure, respiration rate, and pulse)
- ECOG performance status (see Appendix 2)
- Clinical blood tests (see Section 6.5)
- Serum- or urine pregnancy testing (to be performed monthly until 120 days after the last administration of study drug) (see Section 8.8.2)

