#### 8.1.7 Further adverse event and serious adverse event definitions

Wherever possible, a specific disease or syndrome rather than individual associated signs and symptoms should be identified. However, if an observed or reported sign or symptom is not considered a component of a specific disease or syndrome by the Investigator, it should be recorded as a separate AE.

Laboratory data are to be collected as stipulated in Section 6.5. Clinical syndromes associated with laboratory abnormalities are to be recorded as appropriate (e.g., diabetes mellitus instead of hyperglycemia).

Scheduled hospitalizations or elective surgical for a pre-existing condition that is unrelated to the disease under study and has not worsened are not considered SAEs.

Prolongation of a scheduled hospitalization is considered an SAE.

Complications associated with scheduled procedures are considered AEs or SAEs.

Progression of disease is considered an efficacy outcome parameter and should not be captured as an AE or SAE unless its outcome is death.

Adverse events, that occur following the execution of the ICF but prior to dosing must be recorded in the medical history page of the eCRF; if serious, these must be reported as SAEs as described in Section 8.4. Adverse events, including SAEs, that occur after patients receive any anti-cancer therapy in the follow-up period, other than the study-defined treatments, will not be recorded as AEs or SAEs.

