## Appendix 1 Schedule of Assessments

Tests & Procedures / Visit Name	Pre- Screening Visit	Screening Visit	Cycl	le 1	Cycle 2+	End of Treatment Visit	30-day Safety Follow-up	Overall Survival Follow-up
Day	NA	0	1	15	1	Within 7 days after last dose of derazantinib or decision to permanently stop dosing	30+ days after the last dose of derazantinib	At least every 3 months from date of last dose of derazantinib
Window	NA	-28 to -1	0	± 3 days	± 3 days	NA	NA	±14 days
Written informed consent	X 	X 						
Medical history	X	Х						
QLQ-C30, QLQ-BIL21, EQ-5D, G-SET/HTI questionnaires (prior to seeing physician)			$\mathbf{X}^2$		$X^2$	$X^2$	X 	
Physical examination		X	Х	X	Х	X	Х	
Complete opthalmological examination		х			X 	х	X 	
ECOG performance status	Х	Х	Х	X	Х	Х	Х	
Vital signs 		Х	Х	Х	Х	Х	Х	
12-Lead ECG, in triplicate		X 	X 	X 	X 	X 		
Blood for clinical blood tests 		Х	Х	Х	Х	X	Х	
Blood for serum pregnancy test		X 	X 		$X^7$	X 	X 	
Blood for tumor markers, biomarkers, and ctDNA			X 		X 	X 		
Blood for pharmacokinetics			X9	X 	X9			
Urine for Pharmacokinetics					X 			
Tumor's genomic status 	Х							
Tumor measurement and staging		X 			X 	X 		
Concomitant medications		X 	X 	Х	X	Х	Х	
Adverse events assessment			Х	Х	X	Х	Х	
Derazantinib capsule dispensing 			Х		Х			
Derazantinib capsule accountability					Х	Х		
Survival contact 								Х

For footnotes see next page.

-  Consent can be obtained greater than 28 days prior to first dose and does not have to be repeated unless an updated, approved consent form is available. A patient can consent for tissue analysis and the full study separately or at the same time.

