#### 3.2.8.1 Adverse Events

AEs will be coded using the MedDRA and assigned the grades (severities) based on NCI CTCAE, Version 4.03. For AEs not listed in the NCI CTCAE version 4.03, a similar grading system should be used as follows:

- Grade 1: Mild AE
- Grade 2: Moderate AE
- Grade 3: Severe AE
- Grade 4: Life-threatening or disabling AE
- Grade 5: Death

A treatment-emergent adverse event (TEAE) is defined as an AE with start date on or after the date of first dose and up to 30 days after last dose of study treatment (or until the start of a new anticancer therapy, whichever occurs earlier).

An overall TEAE incidence summary table will be produced and will include the number and percentage of patients with any TEAE, with any TEAE assessed by the Investigator as related to drug (related/not related), and with any serious TEAEs, drug-related serious TEAEs, TEAEs leading to permanent study drug discontinuation, drug-related TEAEs leading to permanent study drug discontinuation, TEAEs leading to study drug dose reduction or interruption, TEAEs leading to study drug dose reduction or interruption, drug-related TEAEs leading to study drug dose reduction or interruption, drug-related TEAEs leading to study drug dose reduction or interruption, drug-related TEAEs leading to study drug dose reduction or interruption, drug-related TEAEs leading to study drug dose reduction or interruption TEAEs leading to death, drug-related TEAEs leading to death will be summarized. The number of events will also be displayed.

For all event types listed above in the overall AE incidence summary table, tabulations by SOC and PT will also be produced. These will be presented by SOC and PT, sorted by decreasing frequency. Furthermore, TEAE, and drug-related TEAEs will also be summarized by SOC, PT, and maximum CTCAE grade, and sorted by decreasing frequency. Patients with more than one AE within a particular SOC are counted only once for that SOC. Similarly, patients with more than one AE within a particular PT are counted only once for that PT. For summaries by maximum CTCAE grade, patients with multiple AEs within a particular SOC or PT will be counted under the category of their most severe AE within that SOC or PT. AEs with missing CTCAE grade will be included in the missing counts.

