#### 3.2.8.2 Laboratory Variables

Local laboratory results will only be listed.

Central laboratory results will be summarized with descriptive statistics at each scheduled time and for the change from baseline. Repeated or unscheduled tests will not be summarized for each scheduled visit (with the exception of baseline which may include unscheduled visits). Baseline values and values at each visit for each laboratory parameter collected be descriptively summarized and plotted over time using a boxplot.

Laboratory data will also be summarized using shift tables where appropriate. Each patient's continuous laboratory safety parameter values will be flagged as "low", "normal", "high" or "missing" relative to the normal ranges. Each patient's categorical laboratory safety parameter values will be flagged as "abnormal" or "normal". This categorical data will be summarized in shift tables comparing the minimum post-baseline value, maximum post-baseline value and all other relevant post-baseline visits with those at the baseline visit. Note that minimum post-baseline will only be displayed in the instances where there is a range with lower limit of normal (LLN) >0. For parameters that have gradings for both low and high values, low and high will be summarized separately.

In the shifts of low values, any high values will be classified as normal and the worst low grade will be summarized. And in the shifts of high values, any low values will be classified as normal and the worst high grade will be summarized.

In addition, CTCAE grade and hyperphosphatemia grade will be summarized. Shift tables of grade from baseline to maximum or minimum on-treatment as applicable will be produced.

Since hyperphosphatemia is not defined by CTCAE v. 4.03, as per protocol hyperphosphatemia is defined as:

Grade 1: > upper limit of normal (ULN) to < 7.0 mg/dL (<2.26 mmol/L)

Grade 2: Non-invasive intervention required (e.g., withhold drug or modify dose) or between 7.0 - 9.0 mg/dL (2.26 - 2.90 mmol/L)

Grade 3: Severe or medically significant, but not immediately life threatening, or > 9.0 - 10.0 mg/dL (> 2.90 - 3.23 mmol/L)

Grade 4: Life-threatening consequences, urgent intervention indicated e.g., dialysis, or > 10.0 mg/dL (> 3.23 mmol/L)

Central and local laboratory results will be included in by-patient listings and will include CTCAE grade and hyperphosphatemia grade at each visit, as well as change from baseline at each visit.

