# Hy's law

Patients who have elevated alanine aminotransferase (ALT), aspartate aminotransferase (AST), and total bilirubin post baseline will be summarized descriptively as follows and Hy's law cases identified.

- ALT and AST: > 3x ULN, > 5x ULN, > 10x ULN, > 20x ULN
- Total bilirubin >2x ULN
- ALT or AST: > 3x ULN and Total bilirubin >2x ULN

Plots of ALT and AST vs. Total bilirubin by module will also be produced with reference lines at 3×ULN for ALT, AST, and 2×ULN for total bilirubin. In each plot, peak total bilirubin x ULN will be on the vertical axis and peak ALT or AST x ULN will be on the horizontal axis.

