#### 3.2.8.5 ECOG

ECOG performance status will be summarized in a shift table, which will summarize values at baseline, each visit and the maximum values during the study.

All ECOG performance assessments will be provided in a by-patient listing.

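### The worst-value laboratory, Hy's law and ECOG summaries have no end date, whereas adverse-event counting stops when a new anticancer therapy starts

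*Protocol*

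**What the plan says.** **Adverse events.** Protocol 5.5 states that when another anticancer therapy begins within the safety follow-up period, "the follow-up for AEs will cease, beginning the first day of the new therapy". Protocol 8.1.7 leaves unrecorded any adverse events, serious ones included, "that occur after patients receive any anti-cancer therapy in the follow-up period". SAP 3.2.8.1 counts an event as treatment-emergent from first dose "up to 30 days after last dose of study treatment (or until the start of a new anticancer therapy, whichever occurs earlier".

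**What is still collected.** Directly after the stop rule, Protocol 5.5 lists clinical blood tests, vital signs and ECOG at the 30-day Safety Follow-up visit, with no exception for patients who have switched. Protocol 6.5 schedules the safety laboratory panel there and sends all samples to a central laboratory. Appendix 1 times the visit at "30+ days after the last dose of derazantinib" and gives its window as not applicable. SAP 3.1.3 tabulates data under the recorded visit even when the assessment is out of window.

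**How these data are summarized.**
- Laboratory shift tables (SAP 3.2.8.2) are built by "comparing the minimum post-baseline value, maximum post-baseline value and all other relevant post-baseline visits with those at the baseline visit".
- For raised ALT and AST, the Hy's law text reads "and total bilirubin post baseline will be summarized descriptively as follows and Hy's law cases identified". The accompanying plots use each patient's peak values.
- ECOG (SAP 3.2.8.5) is shown at baseline, "each visit and the maximum values during the study".
- CTCAE-grade and hyperphosphatemia-grade shifts (SAP 3.2.8.2) run to the worst on-treatment grade. The SAP does not define on-treatment.

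SAP section 4, which lists changes from the planned analysis, does not mention the difference.

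**The concern.** The plan already takes the position that an event arising after a switch is not to be counted against derazantinib. The worst-value laboratory and ECOG outputs do not carry that decision over. A raised ALT or bilirubin drawn at the 30-day visit, after the next regimen has started, is outside the adverse-event tables but may be the patient's maximum in the shift table, the Hy's law table and the peak plot.

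The study has one arm, so no comparator would show that late values are inflating these tables. Protocol 7.8 names increased transaminases as an important identified risk, and SAP 3.2.8.1 lists transaminase elevations among the events of special interest. Hy's law tables usually hold very few patients, so one wrongly attributed case can alter how they are read.

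**Working it through.** No sample-size, power or error-rate figure is involved. The check sets the observation windows side by side.

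| Output | Source | Stated end | Cut at new therapy | Can a post-switch value from the 30-day visit enter? |
|---|---|---|---|---|
| Treatment-emergent events | SAP 3.2.8.1 | last dose + 30 days | yes | no |
| Laboratory low/normal/high shift, minimum and maximum | SAP 3.2.8.2 | none | no | yes |
| CTCAE-grade and hyperphosphatemia-grade shift | SAP 3.2.8.2 | on-treatment, undefined | not stated | cannot be decided from the text |
| ALT/AST/bilirubin thresholds, Hy's law, peak plots | SAP 3.2.8.2, Hy's law | none | no | yes |
| ECOG maximum | SAP 3.2.8.5 | the study | no | yes |
| Laboratory tables by visit | SAP 3.2.8.2 | by visit | no | yes, under its own visit label |
| Vital signs by visit | SAP 3.2.8.3 | by visit, no worst value | no | yes, under its own visit label |

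**What has to happen for an output to change.** The patient starts a new therapy before the 30-day visit, attends it, has a central sample or an ECOG score recorded there, and that value is worse than every earlier one (or, for a minimum, lower). Local laboratory results are only listed. Under SAP 3.1.3, unscheduled visits other than baseline are also only listed. After the 30-day visit the schedule holds only survival contact and pregnancy testing. At most about one scheduled sample per patient is therefore at issue.

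**Why Hy's law is the sensitive output.** The plots put peak ALT or AST against peak total bilirubin, with reference lines at 3 and 2 times the upper limit of normal, and do not require the two peaks to share a date. A patient with ALT above 3 × ULN on derazantinib, and bilirubin above 2 × ULN only at the 30-day visit on the next regimen, falls in the upper right quadrant. Nothing in the text removes that patient.

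**Size.** The planned total is 100 (Substudy 1) + 43 (Substudy 2) = 143 patients. The share who switch before the 30-day visit is not given, so a range is assumed:

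- 5%: 143 × 0.05 = 7.15, about 7
- 10%: 143 × 0.10 = 14.3, about 14
- 20%: 143 × 0.20 = 28.6, about 29
- 30%: 143 × 0.30 = 42.9, about 43

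For each assumed rate this is a ceiling on the patients affected, because the other conditions must also hold. Switching is plausible: in the earlier phase 1/2 study (Protocol 1.5.3), 69 + 24 = 93 of 119 patients (78.2%) stopped for radiological or clinical progression. That figure says nothing about whether or when they began another therapy.

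**The case against.** The best opposing case has several parts, and some of them stand.

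- **Not every laboratory summary is open-ended.** This stands. The grade shifts are restricted to on-treatment, so the defect there is an undefined term.
- **Tables by visit mislead no one.** This stands. The 30-day visit has its own label, vital signs have no worst-value output, and the questionnaires are summarized by visit.
- **The shift text leaves room to choose relevant visits, and listings allow any case to be traced.** The first half applies to the visit columns, not to the minimum and maximum. Tracing helps a careful reader but does not correct the table.
- **An inclusive worst-value rule is conservative and keeps late liver signals.** This is a fair choice in principle, but the SAP does not state it as a choice, and it contradicts the rule used for events. The fix must keep late values visible.
- **Background abnormality blurs these counts anyway.** Protocol 4.2 admits AST/ALT up to 5 × ULN with liver metastases and bilirubin up to 2 × ULN. This is true, and it limits what any window can achieve, but it is no reason to add values from another regimen.
- **The event side is not perfectly closed.** Protocol 10.3 also counts baseline events that worsen or are later judged drug-related up to the end of the study. The SAP definition does not include this, so the comparison here is with the SAP.
- **The tables are descriptive and no decision rule uses them.** This stands and bounds the severity.

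A reader might infer that the next therapy's toxicity will in fact be tabulated as derazantinib's, or that a particular number of false Hy's law cases will follow. The documents support neither. They show that it can happen, and they give no switching rate and no rate of liver abnormality after a switch.

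**Conclusion.** The mismatch is real and limited. The minimum/maximum laboratory shifts, the Hy's law summary and peak plots, and the ECOG maximum can include a value from the 30-day visit taken after another anticancer therapy has started. The event tables exclude that period. For the two grade-shift tables, the window cannot be determined because on-treatment is undefined.

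The number of patients affected cannot be derived from the documents; the range above rests wholly on the assumed 5% to 30%. The primary endpoints are not touched. The point should still be corrected, because it bears on the main hepatic-safety output of a single-arm study and can be settled by a rule on dates.

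**What to change.** In SAP 3.2.8, state one window for the laboratory minimum/maximum shifts, the grade shifts, the Hy's law summary and peak plots, and the ECOG maximum: from first dose to 30 days after last dose, or to the start of a new anticancer therapy if earlier. Define on-treatment as that window. List values outside it separately, flagged, so that a late hepatic signal stays visible. Tables by visit, vital signs and questionnaires need no change.

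Ending the window at the 30-day visit itself would not do, since that visit has no upper limit and the laboratory and event periods would still differ.

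**Cost.** A definition, short edits in SAP 3.2.8.2 and 3.2.8.5, and a date filter. The start date of new therapy is already needed for the treatment-emergent rule and for the PFS sensitivity analysis in SAP Table 5. The drawback is that some late values move from the worst-value summaries to the listings. These include samples drawn after day 30 in patients who have not switched, and possibly a delayed derazantinib effect. Samples from the 30-day visit still appear in the tables by visit.

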## 5.6 Survival Follow-up (at least every 3 months ± 14 days)

Patients will be followed for survival from the day of the last dose of derazantinib. All patients and/or family will be contacted at 3-month intervals ( $\pm$  14 days) and record the patient status as Alive (date); Dead (date); Alive, but withdrew consent for further follow-up; Lost to Follow Up. Survival updates may be made more often than every 3 months if the patient is seen at the investigational site for other reasons and for study level survival sweep(s). Survival follow-up will continue until the study has completed or other discontinuation criteria are met.

Note: Survival follow-up can be done either as an office visit, over the telephone, or by collection of public records in accordance with local laws.

#### 5.7 Discontinuation from the treatment or study

#### 5.7.1 Patient discontinuation from treatment

Patients will be removed from the study treatment at any time if they meet any of the following criteria:

- Documented radiographic progression of disease
  - Radiographic progression must be confirmed by central radiology prior to treatment discontinuation if progression is seen on the first or second posttreatment scan
  - Patients may remain on study treatment if, in the opinion of the Investigator and with the agreement of the Medical Monitor, they continue to derive benefit from derazantinib

- Central negative or unconfirmed FISH test result for an *FGFR2* fusion in patients enrolled based on a locally-documented *FGFR2* fusion positive
  - If the central FISH test could not be performed for technical reasons and the patient did not experience radiographic progression, the patient may be allowed to continue the study treatment
  - If the central FISH test result is negative for an *FGFR2* fusion, the patient should be discontinued from the study treatment, other than in exceptional cases when, based on ethical considerations and an individual benefit-risk assessment, discontinuation of the patient from the study treatment is considered unacceptable
- Documented clinical progression of disease
- Clinical unacceptable toxicities despite optimal treatment or dose reduction
- Pregnancy (see Section 8.8.2).
- Patient decision to discontinue treatment and study visits
- Withdrawal of consent from treatment and study follow up calls
- Non-compliance with any part of the study, as assessed by the Investigator or Medical Monitor
- Investigator's decision after discussion with the Medical Monitor or designee
- Death

## 5.7.2 Patient discontinuation from the study

Patients who discontinue from study treatment will still be followed for survival either through direct contact or collection of public records (e.g., death certificate) in accordance with local laws, unless they meet any of the following criteria:

- Withdrawal of consent for long-term (survival) follow-up
- Lost to follow-up
- Death

# 5.8 Study discontinuation

The Sponsor reserves the right to temporarily or permanently discontinue the study at any site or at any time. Reasons for study discontinuation may include, but are not limited to, the following:

- Safety concerns
- Poor enrollment
- Non-compliance with the protocol, GCP guidelines, or other regulatory requirements by the Investigator(s)
- Request to discontinue the study by a regulatory or health authority
- Discontinuation of product development
- Manufacturing difficulties/concerns

The Sponsor and/or designee will promptly inform all Investigators and the appropriate regulatory authorities if the study is suspended or terminated for safety reasons. In the event of such a study termination, the Investigator must notify the IRB or IEC, as appropriate.

#### **6 STUDY PROCEDURES**

#### 6.1 Medical history and prior/concomitant medications

Medical history will include but not be limited to the following:

- Demography: year of birth, gender, race (unless local regulations do not permit), ethnicity (US patients)
- Clinically significant prior diagnoses, surgeries, and current medications
  - Medications used within 30 days prior to the first dose of derazantinib and throughout the treatment period should be reported
- Prior cancer history, current cancer diagnosis, tumor stage at the time of diagnosis and screening, previous anti-cancer therapy including dates, duration and outcome of treatment, previous radiation therapy including anatomic site, dose and dates of treatment, previous cancer-related surgical procedures, including type of the procedure and dates.
  - For all patients with confirmed *FGFR2* GAs eligible for the study (i.e., either *FGFR2* fusions, or mutations/amplifications listed in Appendix 8), detailed records of prior systemic treatments and responses will be collected in the EDC system;
  - All eligible (enrolled and dosed) patients will be asked to forward CT/MRI scans performed during prior therapy(ies) to the central imaging laboratory.

